### Investigators Experience

#### **INSTRUCTIONS:**

Provide a brief description of the investigators experience in working with this population in the clinical and research arena.

If this study will be done in a foreign country, add their experience working within the foreign country.

## Brief Summary/Abstract

### INSTRUCTIONS:

Provide a very brief summary or abstract of this study (500 words or less). Include the purpose or hypothesis, a brief description of the experiment, and plans for data analysis.

DO NOT Reference the sponsors protocol here.

If you plan to deviate from the Sponsor's protocol in any way, such as not doing certain sub-studies, include a description of those deviations in this summary.

For those studies where data will be analyzed collaboratively by multiple sites doing a similar study for which there is no sponsors/common protocol (Collaborative Site Analysis Study) include a description of the common scientific goals/procedures/data points.

### Answer/Response:

Pulmonary function is compromised following upper abdominal surgery. The incidence of post-operative pulmonary complications following upper abdominal surgery ranges between 17% and 88%, and it is a common cause of morbidity and mortality. Physicians order Incentive Spirometry (I.S.) and EzPAP® lung expansion therapy following surgery to encourage improved alveolar ventilation and to reduce risks of post-operative pulmonary complications associated with inhomogeneous distribution of ventilation during deep breathing inspiratory efforts. The primary purpose of this study is to determine if there is a difference in regional distribution of ventilation when comparing resting tidal ventilation with Incentive Spirometry (I.S.) and EzPAP® lung expansion therapy in healthy adult human subjects. We are also interested in determining if regional redistribution of ventilation is time dependent. Lung volume areas of interests include ventral, mid-ventral, mid-dorsal, and dorsal regions. Our null hypotheses is that there is no difference.

A convenience sampling of study participants will be invited to participate in our descriptive observational study. Study participants will be randomly allocated to receive I.S. or EzPAP® therapy after informed consent has been obtained. Electrical Impedance Tomography (EIT) monitoring will be used to visualize and measure regional distribution of ventilation during lung expansion therapy.

EIT lung monitoring and descriptive data will be presented as number (%), mean (SD), or median (IQR) as appropriate. To test our primary hypothesis, the difference between continuous level data will be analyzed with one-way multivariate analysis of variance. This is a proof of concept study that will include 30 human subjects. Statistical significance is set at  $\leq 0.0125$ . We have created a password protected SPSS file (SPSS v.23; Chicago, IL) that will be used for this study's data entry codebook and statistical output generator.

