**Answer/Response:**

**PRIMARY NULL HYPOTHESIS:**

There is no difference in regional distribution of ventilation when comparing Incentive Spirometry (I.S.) lung expansion therapy to EzPAP® lung expansion therapy in healthy adult human subjects

**Alternative hypothesis:** There is a difference in regional distribution of ventilation when comparing Incentive Spirometry (I.S.) lung expansion therapy to EzPAP® lung expansion therapy in healthy adult human subjects?

- Independent variable
  - Lung expansion therapy
    1. Incentive Spirometry

2. EzPAP®

- Dependent variables
  - Regional distribution of ventilation areas of interest
    1. Ventral end-expiratory lung volume impedance
    2. Mid-ventral end-expiratory lung volume impedance
    3. Mid-dorsal end-expiratory lung volume impedance
    4. Dorsal end-expiratory lung volume impedance
- Statistical analysis
  - Frequency (n) and percentage (%) will be used to report descriptive categorical level data.
  - Shapiro-Wilk test of normality will be applied to evaluate distribution of continuous level data. Normally distributed data will be presented as mean and standard deviation and 95% confidence interval. Effect size will be reported as Cohen's *d*.
  - Non-normally distributed data will be reported as median and interquartile range. Effect size will be reported as *r*.
  - Independent samples t-test will be applied to normally distributed continuous data to compare group means, and Mann Whitney-U test will be applied to non-normally distributed data.
  - Statistical significance set a  $P$  (2-tailed)  $\leq .0125$  to reduce risk of Type I error.

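### The abstract and the statistical section name different primary tests (one MANOVA, or four regional t/Mann-Whitney tests) and different primary contrasts, and nothing says which decides the study

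*Combined protocol and SAP*

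**What the plan says.** **Brief Summary/Abstract.** The stated purpose is to look for a "difference in regional distribution of ventilation when comparing resting tidal ventilation with Incentive Spirometry (I.S.) and EzPAP® lung expansion therapy". On analysis it says "To test our primary hypothesis, the difference between continuous level data will be analyzed with one-way multivariate analysis of variance", and then "Statistical significance is set at" 0.0125. It lists four regions: "Lung volume areas of interests include ventral, mid-ventral, mid-dorsal, and dorsal regions".

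**Hypothesis to be Tested.** The purpose is again eupneic (resting) ventilation against the two therapies. The formal primary question is an ambiguous version of the same comparison.

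**Statistical Considerations, question 2.** The focus is now I.S. against EzPAP.

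**Statistical Considerations, question 4 (primary variable analysis).** The null is no difference between I.S. and EzPAP. Four regional end-expiratory impedance variables are listed. The rule for choosing a test is "Shapiro-Wilk test of normality will be applied to evaluate distribution of continuous level data", followed by "Independent samples t-test will be applied to normally distributed continuous data to compare group means, and Mann Whitney-U test will be applied" otherwise. The threshold is two-tailed 0.0125, given only as a means "to reduce risk of Type I error". MANOVA does not appear.

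**Statistical Considerations, question 5.** The secondary analysis is declared to be the same.

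No section puts the MANOVA first with regional follow-up, gives one analysis precedence, states an overall alpha, or says how four regional results become one answer.

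**The concern.** A joint test of four outcomes and a set of four single-outcome tests reject in different circumstances. With both on file as primary, one can show a difference while the other does not. The study is open-label, and nothing in the plan prevents the choice being made once results are known.

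The threshold adds to the problem. A value of 0.0125 looks like a correction for four tests, yet the abstract attaches it to a MANOVA, which already treats the four regions jointly. In a study of 30 subjects the power lost that way matters.

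The test also cannot be settled apart from the contrast. A one-way MANOVA with therapy group as the factor compares I.S. with EzPAP. It does not by itself compare rest with therapy, and neither do independent-samples tests.

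**Working it through.** **Inputs from the plan:** 30 subjects in total (Subjects, question 1); four regional variables; threshold 0.0125 two-tailed. No effect size, SD, power or allocation ratio is given.

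**Assumptions:** 15 per arm, normal data, unit SD, equal correlation r between regions, and the effect patterns below.

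**Step 1. The plan's threshold.** 0.05/4 = 0.0125 exactly. Four such tests sum to 4 × 0.0125 = 0.05; if independent, 1 − (1 − 0.0125)^4 = 0.0491. So 0.0125 is what four separate tests need if the overall level is 0.05. That 0.05 is an inference.

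**Step 2. MANOVA.** With two groups it is Hotelling's T², where T² = (15·15/30) d′S⁻¹d, and F = T²·25/(4·28) on 4 and 25 df. The critical F is 3.97 at 0.0125 and 2.76 at 0.05. Power comes from the non-central F with ncp = 7.5 δ′R⁻¹δ. At r = 0.5, R⁻¹ = 2(I − 0.2J), with J the matrix of ones:

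- all regions +0.8 SD: 7.5 × 2 × (2.56 − 0.2 × 10.24) = 7.68
- dorsal only +1.0 SD: 7.5 × 2 × (1 − 0.2) = 12.0
- opposite shifts (−0.5, −0.25, +0.25, +0.5 SD): 7.5 × 2 × 0.625 = 9.375

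Power at 0.05 and then at 0.0125 is 50% and 27%, 71% and 48%, and 59% and 35%. The stricter level costs 23, 23 to 24, and 24 points.

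**Step 3. Four tests.** The null is rejected if any region has P ≤ 0.0125 (t on 28 df, critical value 2.669). Power and disagreement were simulated; disagreement compares the two analyses with both at 0.0125.

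| r | Pattern | Any of four at 0.0125 | MANOVA at 0.0125 | MANOVA at 0.05 | Verdicts differ |
|---|---|---|---|---|---|
| 0.5 | all +0.8 SD | 64% | 27% | 50% | 37% |
| 0.5 | dorsal only +1.0 SD | 55% | 48% | 71% | 26% |
| 0.5 | opposite shifts | 26% | 35% | 59% | 24% |
| 0.7 | all +0.8 SD | 57% | 20% | 41% | 37% |
| 0.7 | dorsal only +1.0 SD | 55% | 76% | 91% | 32% |
| 0.7 | opposite shifts | 25% | 63% | 84% | 44% |

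A wider grid (r from −0.3 to 0.8, other effect sizes) gave disagreement from about 10% to 62%.

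**Step 4. No true difference.** If either analysis could be claimed, the bound on the false-positive rate is 0.05 + 0.0125 = 6.25%. Simulated values are about 5.1% at r = 0.3 and 4.4% at r = 0.7.

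**Step 5. Contrast against test.**

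| Section | Contrast | Test named |
|---|---|---|
| Abstract | rest versus therapy | one-way MANOVA |
| Hypothesis to be Tested | rest versus therapy (formal question ambiguous) | none |
| Statistical Considerations, question 2 | I.S. versus EzPAP | none |
| Statistical Considerations, question 4 | I.S. versus EzPAP | t-test or Mann-Whitney by region |

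Only the last row pairs a contrast with a test that addresses it.

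**The case against.** **The abstract is only a summary.** Question 4 is the dedicated answer on primary analysis and is probably the operative text. That is fair, but the form asks the abstract to include plans for data analysis, the abstract ties the MANOVA expressly to the primary hypothesis, and no rule of precedence is given.

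**A reader might infer that two tests are set for one and the same hypothesis.** The documents do not support that. Both hypotheses are called primary, but one concerns rest versus therapy and the other I.S. versus EzPAP. Exchanging one test sentence for the other would leave the contrast conflict in place.

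**A reader might infer that 0.0125 is wrong for a MANOVA.** It is not; it gives a valid test at that level. It is needlessly strict only if 0.05 overall was meant, which the plan does not say.

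**A reader might infer that the four regional tests are plainly the better choice.** Step 3 does not show this. At r = 0.5 the MANOVA at 0.05 beats them for a dorsal-only shift (71% versus 55%) and for opposite shifts (59% versus 26%). It loses when all regions move together (50% versus 64%). For a question about regional redistribution, the first two patterns matter at least as much as the third.

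**The sizes are hypothetical.** This stands. Effects, correlation and allocation are assumed, and the simulation used t-tests throughout although the plan may switch to Mann-Whitney. Four separate tests are also inferred, from four variables plus univariate methods; the plan does not give the count.

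**It is a 30-subject proof-of-concept study with no power analysis.** True, and it tempers the consequences. The plan still sets a hypothesis test and a threshold, so what counts as its primary result should be fixed.

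**Conclusion.** The contradiction is real. Two analyses are presented as primary, attached to different contrasts, with one unexplained threshold and no rule for choosing. Under the stated assumptions the two analyses at 0.0125 give different answers in about 24% to 44% of trials in the tabulated scenarios, and neither is always more powerful. If 0.05 overall is intended, holding the MANOVA to 0.0125 costs about 23 to 24 points of power at r = 0.5.

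The harm is conflicting verdicts and lost power. A reader might infer serious error inflation from having two chances to reject, but at about 4.4% to 5.1% for r = 0.7 to 0.3 the calculation does not support that.

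**What to change.** Before data are analysed:

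1. State one primary contrast, in the same words, in the abstract, Hypothesis to be Tested, and Statistical Considerations questions 2 and 4.
2. State the overall alpha and how 0.0125 follows from it.
3. Name one primary test that addresses that contrast. For I.S. versus EzPAP, either of these is sound:
   - **(a)** The four regional tests at 0.0125 each, with the primary null rejected if at least one region has P ≤ 0.0125. Delete the MANOVA from the abstract, or call it supportive with no claim of its own.
   - **(b)** One MANOVA at the overall alpha (0.05 if that is intended), with the four regional tests at 0.0125 only if it is significant.
4. If rest versus therapy is kept as primary, name a within-subject analysis for it, since neither test now in the plan addresses that contrast by itself.

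The choice between (a) and (b) belongs to the investigators and should follow the pattern they expect. Option (a) gives up power when one region moves alone or regions move in opposite directions, even at moderate correlation. Option (b) gives up power when all regions shift together. The cost is a few sentences across four sections, with no extra subjects or measurements.

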## Background

### 1. Provide the scientific background, rationale and relevance of this project.

#### INSTRUCTIONS

- This should include a referenced systematic evidenced-based review when possible.
- If this study involves qualitative research explain the major constructs of your study.

- Do not state in this section what you plan to do in this study. This information should be entered later under “What will be done in this protocol?”
- Do not include the bibliography in this section.
- For studies submitted under the Expedited review criteria, this section need not be more than a few pages.

**Answer/Response:**

Pulmonary function is compromised following upper abdominal surgery. The incidence of post-operative pulmonary complications following upper abdominal surgery ranges between 17% and 88%, and it is a common cause of morbidity and mortality.

Lung expansion therapy with I.S. is commonly ordered prophylactically in attempt to improve pulmonary function and reduce post-operative pulmonary complications. However, a recent Cochrane Review meta-analysis (do Nascimento, JP et al., 2014) reported no statistically significant difference in post-operative clinical complications when comparing Incentive Spirometry to either no respiratory treatment (RR 0.59, 95% CI 0.30 – 1.18), or to deep breathing exercises (RR 0.67, 95% CI 0.04 – 10.50). The authors rated the GRADE quality of evidence as “Low” and concluded that there is no evidence that Incentive Spirometry is effective in preventing post-operative pulmonary complications following upper abdominal surgery. Further research with improved study design is necessary to determine if I.S. or other forms of lung expansion therapy (EzPAP®) offers any clinical benefit.

Evaluating the effectiveness of lung expansion therapy relies upon global parameter measures such as pulse oximetry oxygen saturation and/or arterial blood gas measurements, chest wall auscultation, and assessment of sputum expectoration following therapy sessions. These global parameters do not provide the sensitivity necessary to evaluate regional lung function responses to therapy, as can be viewed with a chest x-ray or CT image. These diagnostic images provide a static view for regional lung volume assessment. They also rely upon the use of radiation. In our study, we will use Electrical Impedance Tomography (EIT) monitoring to measure regional distribution of ventilation during I.S. and EzPAP® lung expansion therapy to better understand how air travels through ventral, mid-ventral, mid-dorsal, and dorsal lung regions and to determine if redistribution of lung volume is time dependent. This non-invasive, non-radioactive/non-radiation producing, technology will provide real time quantifiable data that may be used to explore whether there is a difference in preferential regional distribution of ventilation when comparing resting eupneic ventilation to I.S. and EzPAP lung expansion therapy. We will also evaluate whether there is a difference in regional distribution of ventilation measured immediately after the third lung expansion therapy breathing sequence and post-lung expansion therapy session baseline measurement.

### **Hypothesis to be Tested**

**INSTRUCTIONS:**

If this study involves biomedical research clearly state the objectives and hypotheses and clearly define the primary and any secondary outcome measures. If this study involves qualitative research clearly state your research hypothesis or question.

This section should not include information already included in other sections such as background information or information from the procedures section.

**Answer/Response:**

The primary purpose of this study is to determine if there is a significant difference in regional distribution of ventilation when comparing eupneic tidal ventilation to Incentive Spirometry (I.S.) and EzPAP® lung expansion therapy in healthy adult human subjects. Electrical impedance tomography (EIT) will be used to measure regional distribution of ventilation during resting tidal ventilation and during lung expansion therapy.

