**Answer/Response:**

The focus of this study is to use electrical impedance tomography (EIT) monitoring to determine if there is a difference in regional distribution of ventilation when comparing Incentive Spirometry (I.S.) to EzPAP® lung expansion therapy.

Baseline characteristics will be reported as:

- Sex (M/F): n (%)
- Age (years): m (SD)
- Weight (BMI): m (SD) or M (IQR) depending upon normality of data distribution
- Tobacco History: n (%); Never smoked, Current smoker; Former smoker
- Respiratory Related Comorbidities: n (%)

Baseline and post-lung expansion therapy dependent variable metrics will be reported as end-expiratory lung volume impedance (EELI) for each of the following ventilation regions of interest:

- Ventral (Level of measurement- continuous)
- Mid-ventral (Level of measurement- continuous)
- Mid-dorsal (Level of measurement- continuous)
- Dorsal (Level of measurement- continuous)

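### The stated primary purpose is rest versus therapy within each person, but the only primary test planned compares the two devices, and no paired test is named

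*Combined protocol and SAP*

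**What the plan says.** Three places describe a comparison of therapy with rest:

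- The Brief Summary/Abstract gives the primary purpose as finding any "difference in regional distribution of ventilation when comparing resting tidal ventilation with Incentive Spirometry (I.S.) and EzPAP® lung expansion therapy".
- The Background gives the question as "whether there is a difference in preferential regional distribution of ventilation when comparing resting eupneic ventilation to I.S. and EzPAP lung expansion therapy".
- The Hypothesis to be Tested section says the aim is to "determine if there is a significant difference in regional distribution of ventilation when comparing eupneic tidal ventilation to Incentive Spirometry (I.S.) and EzPAP". It adds that measurement takes place at rest and during therapy.

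The statistical section describes a comparison of devices:

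- Statistical Considerations item 2 says the focus is to "determine if there is a difference in regional distribution of ventilation when comparing Incentive Spirometry (I.S.) to EzPAP® lung expansion therapy". It lists end-expiratory lung impedance (EELI) in four regions, at baseline and after therapy.
- Item 4, under the primary null hypothesis, states: "There is no difference in regional distribution of ventilation when comparing Incentive Spirometry (I.S.) lung expansion therapy to EzPAP® lung expansion therapy". Device is the only independent variable. The method is: "Independent samples t-test will be applied to normally distributed continuous data to compare group means", with Mann-Whitney U for non-normal data, two-tailed at 0.0125. No time point is named.
- Item 5 says the secondary analysis is the same as the primary.

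The Abstract names yet another primary test: "To test our primary hypothesis, the difference between continuous level data will be analyzed with one-way multivariate analysis of variance". It states no factor. The Primary Research Question is worded so that the contrast cannot be determined.

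**The concern.** These are two different questions: whether therapy changes regional distribution from rest, and whether two devices differ. The stated purpose asks the first and the analysis plan tests the second. A comparison between devices cannot detect a shift that both devices share. A non-significant result would be a correct answer about the devices, but the declared purpose would have no formal test, only a descriptive report of baseline and post-therapy values.

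The secondary question has the same gap. It compares the measurement immediately after therapy with the one five minutes later in the same person, and item 5 gives it an independent-groups test.

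With two candidate primary contrasts and two candidate primary tests on paper, which one counts as primary could be settled after the data are seen.

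**Working it through.** **Is rest versus therapy within-person?** Statistical Considerations item 1 describes a parallel randomised trial. The I.S. and EzPAP procedure sections each schedule five minutes of resting monitoring before therapy and five minutes after it, in every participant. So it is.

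**Does any named test address it?**

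- The independent-samples t-test and Mann-Whitney U, with device as the factor, do not.
- A one-way MANOVA with device as the factor does not. With rest, I.S. and EzPAP as three levels it would touch the question, but it would treat two values from one person as independent.
- The monitoring section speaks of recording pre-to-post changes. Comparing those changes between arms still removes any shift common to both arms.

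**Inputs.** From the documents: 30 participants, no dropout expected, four regions, alpha 0.0125 two-sided. The documents give no effect size, SD, correlation or power, so there is no power figure to reproduce. The alpha equals 0.05/4, which fits a split over four regions, although the 0.05 is not stated. Assumed for illustration: 15 per arm, a common shift of 0.5 raw SD, and within-person correlation r from 0.3 to 0.9.

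**Planned test when both devices shift a region equally.** The between-device null is then true, so rejection occurs at alpha: 1.25% per region, and 1 − 0.9875^4 = 4.9% for any of four independent regions (at most 4 × 1.25% = 5%). A simulation of 20,000 trials with equal shifts of 0.5 and 1.0 SD gave 1.2–1.3% per region and 4.6–5.2% for any region, on therapy values and on change scores alike.

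**Paired test of the same shift.** The standardised paired effect is dz = 0.5 / √(2(1 − r)), with power from the noncentral t at 0.0125. The unpaired column treats the 30 rest and 30 therapy values as independent (by simulation). It is a univariate analogue of the one-way analysis.

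| r | dz | Paired, 30 pooled | Unpaired, 30 v 30 | Paired, 15 on one device |
|---|---|---|---|---|
| 0.3 | 0.423 | 38% | 24% | 15% |
| 0.5 | 0.500 | 54% | 20% | 22% |
| 0.7 | 0.645 | 80% | 16% | 39% |
| 0.9 | 1.118 | >99% | 8% | 91% |

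For 80% power, the pooled paired test needs a shift of 0.76, 0.64, 0.50 or 0.29 raw SD at these four correlations. With no true shift, the unpaired test's type I error is about 0.3% at r = 0.3 and 0.07% at r = 0.5, against a nominal 1.25%.

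**Multiplicity.** Eight tests at 0.0125 (two contrasts, or two devices, in four regions) allow up to 8 × 0.0125 = 10%, or 1 − 0.9875^8 = 9.6% if independent. Holding 5% over eight tests needs 0.05/8 = 0.00625 each.

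**The case against.** The strongest reply is that item 4 is the operative plan and the purpose statements are loosely worded. Item 4 alone carries the primary-null label, the Study Design section names the I.S. arm as the control, and randomising to devices makes sense only if devices are compared. This is a fair reading. It does not remove the conflict: the purpose statements would still be wrong, item 4 would still lack a time point, and the secondary question would still lack a paired test.

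A second reply is that the intended primary may be the between-device difference in change from rest, for which an independent-samples test on change scores is valid. That is possible, but no section says so, and it would not test the stated purpose.

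Third, the power figures depend on chosen inputs. This stands. At a shared shift of 1.0 SD the unpaired analysis has 93%, 96%, 98% and 99.8% power at the four correlations, so most of the gap closes. Pooling over devices also flatters the paired test, as the last column of the table shows, and power per device would be lower still at 0.00625.

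Fourth, the recordings before and after therapy are both of quiet breathing. Comparing them shows whether an effect persists, not what happens during therapy. This also stands and bears on the fix.

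Finally, this is a small, minimal-risk proof-of-concept study. That may excuse the missing power analysis. It does not excuse a mismatch between hypothesis and test in a plan that sets hypotheses and a significance level.

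**Conclusion.** The concern holds and must be fixed before analysis. Followed as written, the plan leaves both its stated primary purpose and its secondary question without a valid test, and it does not fix which contrast is primary. This conclusion rests on the text alone. That the planned test rejects only at alpha when both devices shift a region equally follows from the design and the stated 0.0125. The power figures are illustrations: they assume the shift and the correlations, and the per-device column also assumes 15 per arm.

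**What to change.** 1. Choose one primary contrast and state it identically in the Abstract, the Hypothesis to be Tested section, the Primary Research Question and Statistical Considerations items 2 and 4. Align the Background, and remove or reconcile the MANOVA sentence. Declare the other contrast secondary.
2. Name the time window. If the purpose is the effect during therapy, define a during-therapy endpoint, because item 2 lists only baseline and post-therapy EELI.
3. Test rest versus therapy within person, by region. A paired t-test or Wilcoxon signed-rank test keeps the plan's Shapiro-Wilk branch. A mixed model with time, arm, arm-by-time and a random subject effect is an alternative.
4. Say whether that contrast is pooled over arms (four tests at 0.0125) or made per device (eight tests at 0.00625).
5. Test I.S. versus EzPAP as the between-arm difference in change from baseline.
6. Replace the item 5 answer with a paired test of the measurement immediately after therapy against the one at five minutes.

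If the sponsor prefers the device comparison as primary, correcting the purpose statements to match settles the primary conflict. Steps 2, 5 and 6 are still needed.

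The cost is protocol wording and a different SPSS procedure. Resting and post-therapy recordings are already scheduled for every participant, so those contrasts need no new participants or recordings. A during-therapy endpoint, if chosen, needs a written definition.
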